1.3 STUDY RATIONALE AND BENEFIT-RISK ASSESSMENT

B cells play a key role and serve multiple functions in the disease pathogenesis through autoantibodies, immune complexes, and amplifying activation of adaptive immune responses (Foster 2007). However, in randomized clinical trials, the Type I anti-CD20 antibodies rituximab and ocrelizumab failed to increase the rate of CRR in proliferative LN (Rovin et al. 2012; Mysler et al. 2013). Incomplete B-cell depletion following rituximab administration is common in lupus patients, and the degree of B-cell depletion following rituximab may be associated with clinical response (Vital et al. 2011; Gomez Mendez et al. 2018). In addition, nonclinical studies have demonstrated that lupus-prone mice have shown resistance to B-cell depletion by anti-CD20 antibodies due to interference in Fc receptor mediated phagocytosis of opsonized cells by lupus serum (Ahuja et al. 2007, 2011).

These lines of evidence provided a scientific rationale to support the Phase II evaluation of obinutuzumab in patients with LN with the hypothesis that greater B-cell depletion would increase response rates above those observed with Type I anti-CD20 monoclonal antibodies such as rituximab or ocrelizumab (Rovin et. al. 2012; Mysler et al. 2013). NOBILITY, a Phase II randomized, double-blind, placebo-controlled, multicenter study, was therefore conducted to evaluate the safety and efficacy of obinutuzumab or placebo infusions at Weeks 0, 2, 24, and 26 in patients with ISN/RPS 2003 Class III or IV proliferative LN treated with MMF and a corticosteroid taper.

NOBILITY met its primary endpoint with a statistically significant difference in CRR between the two treatment groups at Week 52 at a pre-specified two-sided α level of 0.2. At Week 52, 35% of patients in the obinutuzumab group and 23% of patients in the control group achieved CRR (+12% difference; 80% CI: 2.1%, 23%]; p = 0.115). At Week 52, key secondary efficacy endpoints were also met including overall renal response (ORR), defined as obtaining either a complete or partial renal response (PRR), achieved by 56% of patients in the obinutuzumab group and 36% of patients in the control group (+20% difference; 80% CI: [8.9% to 31%]; p = 0.025), CRR excluding urinary sediment, and clinically meaningful improvements in serologic markers of lupus disease activity including anti-dsDNA antibody titer, C3, and C4. An exploratory analysis of the Week 76 efficacy data demonstrated an increasing treatment benefit of

obinutuzumab over control beyond Week 52 (CRR: obinutuzumab 40% vs. control 17%, +22% difference; p = 0.007).

Obinutuzumab was associated with rapid and complete depletion of peripheral B cells in NOBILITY. At Week 2, 88% of obinutuzumab patients had peripheral B cells depleted below the limit of quantitation of a high-sensitivity flow cytometry (HSFC) assay ($\leq 0.441 \text{ cells/}\mu\text{L}$). The NOBILITY regimen resulted in continued B-cell depletion through Week 52, at which point 80% of obinutuzumab patients were depleted to $\leq 0.441 \text{ cells/}\mu\text{L}$. Peripheral B-cell repletion had occurred for the majority of patients by the next measurement at Week 104; only 8% of obinutuzumab patients remained depleted at Week 104. Among obinutuzumab-treated patients, achievement of sustained B-cell depletion through Week 52 was associated with increased renal response.

At the NOBILITY Week 76 data cut, obinutuzumab was not associated with increased serious adverse events (23% of obinutuzumab patients vs. 30% of placebo patients experienced at least one serious adverse event), serious infections (6% vs. 18% incidence), or deaths (2% vs. 7% incidence) compared with placebo. Obinutuzumab was associated with increased non-serious infusion-related reactions (IRRs; 16% vs. 10%). There were no serious IRRs in either group, and no IRRs resulted in the inability to complete the obinutuzumab infusion (following protocol-instructed management, which may have included interruption or slowing of the infusion). No new safety signals were identified.

The Sponsor interprets the efficacy and safety of obinutuzumab in combination with MMF and corticosteroids observed in NOBILITY as being clinically meaningful for the treatment of LN. The current study (CA41705) is being undertaken to confirm the results of NOBILITY and provide long-term data to inform the use of obinutuzumab in proliferative LN.

Given the associations between sustained B-cell depletion and response, and the return of peripheral B-cells observed at Week 104 in NOBILITY, obinutuzumab will be administered in the current study (CA41705) at Day 1 and Weeks 2, 24, 26, and again at 12 months (either Weeks 50 and 52 or Week 52 only), and every 6 months thereafter for patients with an adequate response to treatment, in order to maintain B-cell depletion and increase the degree and durability of clinical benefit with obinutuzumab.

COVID-19 Benefit-Risk Assessment

An assessment was conducted to determine whether there is any impact of the coronavirus disease 2019 (COVID-19) pandemic on the benefit–risk assessment of this study protocol including, but not limited to, the patient population under study and study treatments being evaluated. Based on that assessment, no impact is anticipated, and the existing safety monitoring and management guidelines and risk-mitigation measures provided in the study protocol are considered adequate.

With reference to severe acute respiratory syndrome coronavirus 2 (SARS-CoV-2, the coronavirus strain that causes COVID-19) vaccines, an assessment was conducted to determine whether there is any impact of the SARS-CoV-2 vaccines on the benefit-risk assessment of this study protocol. Given the mechanism of action of obinutuzumab, it is expected that the efficacy of SARS-CoV-2 vaccines may be diminished in patients who are B-cell depleted. The investigator should use clinical judgement to decide on the most suitable timing of vaccination and, where possible, SARS-CoV-2 vaccines should be administered to patients before they start immunosuppressive therapy. The SARS-CoV-2 vaccines may also be administered at any time during the study provided they are non-live vaccines. If administered during the study, the SARS-CoV-2 vaccines are considered concomitant medications. The SARS-CoV-2 vaccines must be administered in accordance with the approved/authorized vaccine label (or equivalent) and official immunization instructions. Based on this assessment, no additional risk mitigation measures related to SARS-CoV-2 vaccination are proposed at this time. The recommendations listed above and the current safety monitoring and management guidelines and risk-mitigation measures provided in the study protocol are considered adequate.

2. OBJECTIVES AND ENDPOINTS

This study will evaluate the efficacy, safety, and pharmacokinetics of obinutuzumab compared with placebo in patients with ISN/RPS Class III or IV LN when added on to standard-of-care therapy consisting of MMF and corticosteroids. Specific objectives and corresponding endpoints for the study are outlined below.

2.1 EFFICACY OBJECTIVES

2.1.1 Primary Efficacy Objective

The primary efficacy objective for this study is to evaluate the efficacy of obinutuzumab (combined treatment groups) compared with placebo on the basis of the following endpoint:

- Proportion of patients who achieve a complete renal response (CRR) at Week 76
 CRR is defined as achievement of all of the following:
 - Urinary protein-to-creatinine ratio (UPCR) < 0.5 g/g
 - Estimated glomerular filtration rate (eGFR) ≥ 85% of baseline, as calculated using the Chronic Kidney Disease Epidemiology Collaboration (CKD-EPI) equation
 - No occurrence of the following intercurrent events:
 - Rescue therapy, treatment failure, death or early study withdrawal

2.1.2 Secondary Efficacy Objective

The secondary efficacy objective for this study is to evaluate the efficacy of obinutuzumab (combined treatment groups) compared with placebo on the basis of the following endpoints.

Key Secondary Endpoints

- Proportion of patients who achieve a proteinuric response at Week 76
 Proteinuric response is defined as achievement of all of the following:
 - UPCR < 0.8 g/g
 - No occurrence of the following intercurrent events:
 - Rescue therapy, treatment failure, death or early study withdrawal
- Proportion of patients who achieve CRR with successful prednisone taper at Week 76, defined as achievement of CRR (as above) at Week 76 with the following:
 - No receipt of prednisone > 7.5 mg/day (or equivalent) from Week 64 through Week 76
- Proportion of patients who achieve an overall renal response (ORR), defined as achievement of either CRR or partial renal response (PRR), evaluated at Week 50 PRR is defined as achievement of all of the following:
 - ≥50% reduction in UPCR from baseline
 - UPCR <1 g/g (or <3 g/g if the baseline UPCR was ≥3 g/g)
 - eGFR ≥ 85% of baseline, as calculated using the CKD-EPI equation
 - No occurrence of the following intercurrent events:
 - Rescue therapy, treatment failure, death or early study withdrawal
- Proportion of patients who experience death or renal-related events through Week 76, defined as the proportion of patients with one or more of the following events:
 - Death
 - Treatment failure (see Section 4.4.4.2)
 - Worsening proteinuria, defined as a confirmed ≥ 50% increase in UPCR to a value ≥ 3
 - Worsening eGFR, define as a confirmed ≥ 30% decrease in eGFR to a value < 60
- Mean change in eGFR from baseline to Week 76
- Change in Functional Assessment of Chronic Illness Therapy—Fatigue (FACIT-F) scale from baseline to Week 76

Supportive Secondary Endpoints

Change in anti-dsDNA titer from baseline to Week 50

- Change in C3 from baseline to Week 50
- Change in Systemic Lupus Erythematosus Disease Activity Index 2000 (SLEDAI-2K) from baseline to Week 76
- Time to onset of CRR over the course of 76 weeks
- Proportion of patients who achieve CRR with serum creatinine criteria at Week 76
 CRR with serum creatinine criteria is defined as achievement of all of the following:
 - UPCR < 0.5 g/g
 - Serum creatinine ≤upper limit of normal (ULN) (as determined by the central laboratory)
 - Serum creatinine not increased from baseline by > 25%
 - No occurrence of the following intercurrent events:
 - Rescue therapy, treatment failure, death or early study withdrawal

2.1.3 Exploratory Efficacy Objective

The exploratory efficacy objective for this study is to evaluate the efficacy of obinutuzumab (combined treatment groups) compared with placebo on the basis of the following endpoints:

- Proportion of patients who achieve the individual components of CRR at Week 76:
 - UPCR < 0.5 g/g
 - eGFR ≥ 85% of baseline, as calculated using the CKD-EPI equation
 - No occurrence of the following intercurrent events:
 - Rescue therapy, treatment failure, death or early study withdrawal
- Proportion of patients who achieve CRR with successful prednisone taper at Week 76, defined as achievement of CRR (as above) with the following:
 - No receipt of prednisone > 7.5 mg/day (or equivalent) from Week 52 through Week 76
- Proportion of patients who achieve CRR at Weeks 36, 50, and 64
- Proportion of patients who achieve proteinuric response at Weeks 36, 50, and 64
- Proportion of patients who achieve ORR at Weeks 36, 64, and 76
- Proportion of patients who achieve CRR on the randomized, blinded therapy at Weeks 106, 132, 158, 184, and 210
- Proportion of patients who achieve proteinuric response on the randomized, blinded therapy at Weeks 106, 132, 158, 184, and 210
- Proportion of patients who achieve ORR on the randomized, blinded therapy at Weeks 106, 132, 158, 184, and 210

- Proportion of patients who achieve CRR with serum creatinine ≤ ULN at Week 76, as defined as achievement of all of the following:
 - UPCR < 0.5 g/g
 - Serum creatinine ≤ULN (as determined by the central laboratory)
 - No occurrence of the following intercurrent events:
 - Rescue therapy, treatment failure, death or early study withdrawal
- Proportion of patients who achieve CRR at Week 76, as defined as achievement of all of the following:
 - UPCR < 0.5 g/g
 - eGFR ≥ 85% of baseline, as calculated using the CKD-EPI equation or ≥ 60 mL/min per 1.73 mL² of body-surface area
 - No occurrence of the following intercurrent events:
 - Rescue therapy, treatment failure, death or early study withdrawal
- Proportion of patients who achieve the CRR serum creatinine criteria at Week 76
 The CRR serum creatinine criteria require achievement of all of the following:
 - Serum creatinine ≤ULN (as determined by the central laboratory)
 - Serum creatinine not increased from baseline by > 25%
 - No occurrence of the following intercurrent events:
 - Rescue therapy, treatment failure, death or early study withdrawal
- Proportion of patients who receive rescue therapy or experience treatment failure by Week 76
- Change in anti-dsDNA titer from baseline to Weeks 4, 12, 24, and 76
- Change in C3 from baseline to Weeks 4, 12, 24, and 76
- Change in C4 from baseline to Weeks 4, 12, 24, 50, and 76
- Change in UPCR from baseline to Weeks 24, 50, and 76
- eGFR slope from Week 12 to Week 76
- Time from first CRR to loss of any response, defined as a failure to meet criteria for either CRR or PRR, during blinded treatment
- Time to LN flare from Week 24, diagnosed if one of the following conditions occurred:
 - eGFR decrease > 20% compared with Week 24 in patients with UPCR > 1 g/g and/or cellular casts;
 - UPCR increase (i) to > 1 g/g if Week 24 UPCR was < 0.2 g/g, (ii) to > 2.0 g/g if Week 24 UPCR was 0.2-1 g/g, or (iii) to doubling if Week 24 UPCR was > 1 g/g; or
 - receipt of rescue therapy, except for corticosteroid-only rescue.

- Time to an unfavorable kidney outcome, defined as the first of the following events: treatment failure, serum creatinine doubling, or death
- Proportion of patients who achieve CRR including urinary sediment at Week 76, defined as achievement of CRR (as above) with urinary RBCs < 10 per high-power field (HPF) without RBC casts
- Cumulative corticosteroid dose from baseline to Week 76
- Change in health-related quality of life (HRQoL) as measured by the 36-Item Short Form Survey, Version 2 (SF-36 v2) from baseline to Week 76
- Change in Physician's Global Assessment (PGA) from baseline to Weeks 24, 50, and 76
- Change in Subject's Global Assessment (SGA) from baseline to Weeks 24, 50, and 76

Additionally, descriptive comparisons of the obinutuzumab treatment groups will be performed on the basis of the renal response endpoints described above.

2.2 SAFETY OBJECTIVE

The safety objective for this study is to evaluate the safety of obinutuzumab (combined treatment groups) compared with placebo on the basis of the following endpoints:

- Incidence and severity of adverse events, with severity determined according to National Cancer Institute Common Terminology Criteria for Adverse Events (NCI CTCAE) v5.0
- Characterization of adverse events of special interest, including, among others, IRRs, neutropenia, infections, and thrombocytopenia
- Change from baseline in targeted vital signs
- Change from baseline in targeted clinical laboratory test results

2.3 PHARMACOKINETIC OBJECTIVE

The pharmacokinetic (PK) objective for this study is to characterize the obinutuzumab PK profile on the basis of the following endpoint:

Serum concentration of obinutuzumab at specified timepoints

2.4 IMMUNOGENICITY OBJECTIVES

The immunogenicity objective for this study is to evaluate the immune response to obinutuzumab on the basis of the following endpoint:

 Prevalence of anti-drug antibodies (ADAs) at baseline and incidence of ADAs posttreatment during the study (only for patients treated with obinutuzumab)

The exploratory immunogenicity objective for this study is to evaluate potential effects of ADAs on the basis of the following measures:

 Relationship between ADA status and efficacy, safety, pharmacodynamic (PD), or PK endpoints

2.5 BIOMARKER OBJECTIVE

The PD objective for this study is to characterize the obinutuzumab-induced changes in circulating B-cells based on the following endpoint:

Total peripheral B-cell count at specified timepoints

2.6 HEALTH STATUS UTILITY OBJECTIVE

The exploratory health status utility objective for this study is to evaluate health status utility scores of patients treated with obinutuzumab on the basis of the following endpoints:

Change from baseline in EuroQol 5-Dimension, 5-Level Questionnaire (EQ-5D-5L) index-based and Visual Analog Scale (VAS) scores at Weeks 0, 24, 50, and 76

STUDY DESIGN

3.1 DESCRIPTION OF THE STUDY

This is a parallel-group, double-blind, randomized, placebo-controlled study comparing the efficacy and safety of obinutuzumab versus placebo among patients with ISN/RPS 2003 Class III or IV LN treated with standard-of-care therapy with MMF and corticosteroids. The study will enroll approximately 252 patients.

Patients must be 18–75 years of age and have active or active/chronic ISN/RPS Class III or IV proliferative LN as evidenced by renal biopsy performed in the 6 months prior to screening or during screening. Patients may have concomitant Class V disease (i.e., Class III/V or Class IV/V). Patients must exhibit significant proteinuria as evidenced by a UPCR ≥ 1 g/g based on a 24-hour urine collection during screening.

Key exclusion criteria include evidence of severe renal impairment, defined by an eGFR <30 mL/min per 1.73 m² of body surface area or ESRD requiring dialysis or transplantation; evidence of active infection; and other safety-related exclusions.

The study consists of the following study periods: screening, blinded treatment, open-label treatment (OLT), and study follow-up (SFU).

3.1.1 Screening

[figure not shown]
Consenting patients will enter a screening period of up to 28 days to be evaluated for eligibility. Procedures at screening will include collecting a medical history, a full physical examination, ECG, and blood and urine sampling. Patients without a renal biopsy within the 6 months prior to screening must undergo a renal biopsy during the screening period.

3.1.2 Blinded Treatment

Randomized patients will receive blinded infusions of obinutuzumab 1000 mg or placebo on Day 1 and Weeks 2, 24, 26, 50, and 52 in three treatment groups according to

Figure 1 below. All patients will receive MMF (see Section 4.3.1.2) and corticosteroids (see Section 4.3.2.1). The primary endpoint, CRR, will be assessed at Week 76. Patients will be offered an optional renal biopsy following the Week 76 assessment (see Section 4.5.9).

Figure 1 Study Schema

All patients receive MMF and a prednisone taper

MMF=mycophenolate mofetil.

Eligibility for subsequent infusions after Week 76 will be determined based on the investigator's assessment of the adequacy of treatment response, need for intensification of therapy, and presence of unmanageable treatment-emergent adverse events according to the guidance provided in Table 1. The randomized treatment assignment will not be revealed during this process and investigators and patients will remain blinded until study unblinding occurs (see Section 3.1.5).

Table 1 Study Treatment after Week 76

Week 76 Response	Clinical Criteria, as Assessed by the Investigator	Subsequent Treatment
Adequate response	 Adequate response to treatment and No need for intensification of therapy and No unmanageable treatment-emergent adverse events 	Continue blinded infusions every 6 months
Inadequate response with some improvement from baseline	 Inadequate response to treatment and Clinically meaningful improvement from baseline in renal parameters or prior clinically meaningful improvement followed by worsening and Current need for intensification of therapy and No unmanageable treatment-emergent adverse events 	Open-label treatment (see Section 3.1.3)
All others	 Primary nonresponse: no clinically meaningful improvement at any time or Early discontinuation of blinded infusions or Receipt of rescue therapy a or treatment failure or Unmanageable treatment-emergent adverse events 	Study follow-up (see Section 3.1.4) and treatment with standard of care at the investigator's discretion

^a Except corticosteroid-only rescue (see Section 4.4.4.1).

Patients who have an adequate response at Week 76 without a need for intensification of therapy or unmanageable treatment-emergent adverse events will continue to receive blinded obinutuzumab 1000 mg or placebo infusions every 6 months beginning at Week 80. Background immunosuppression, including doses of corticosteroids and MMF, will be adjusted at the investigator's discretion beginning at Week 80.

An adequate response is present if all of the following criteria are met:

- UPCR<0.8 g/g or≥50% reduction in UPCR from baseline to subnephrotic levels (< 3 g/g)
- No deterioration in renal function from baseline (eGFR≥85% of baseline)
- No need for high-dose corticosteroids
- No receipt of rescue therapy or treatment failure

Investigators may discuss the adequacy of response and appropriateness of continuing blinded treatment directly with the Medical Monitor if needed.

During continued blinded treatment, investigators should regularly review the study safety plan (see Section 5.1), including the risks associated with obinutuzumab (see Section 5.1.1) and management of specific adverse events that may be related to obinutuzumab (see Section 5.1.3.3), to ensure the patient has not developed a condition that would warrant discontinuation of blinded infusions. Prior to resuming blinded treatment after treatment interruption, investigators should refer to Section 5.1.3.2 to ensure the patient meets the criteria for resuming treatment.

After study unblinding (see Section 3.1.5), no further blinded infusions will be provided through the study protocol. Subsequent access to obinutuzumab may occur through post-trial access (see Section 4.3.4).

After Week 80, patients who, in the opinion of the investigator, experience a loss of response and require intensification of therapy during blinded treatment may be eligible to receive OLT (see Section 3.1.3).

Patients who discontinue blinded infusions and do not enter OLT will enter SFU (see Section 3.1.4).

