3.1.3 Open-Label Treatment

For patients with an inadequate treatment response at Week 76, open-label treatment with obinutuzumab will be provided if all of the following criteria are met at Week 76:

- Inadequate treatment response
- Clinically meaningful improvement from baseline in renal parameters or prior clinically meaningful improvement from baseline followed by worsening
- Need for intensification of therapy
- No unmanageable treatment-emergent adverse events
- No rescue therapy (except corticosteroid-only rescue; see Section 4.4.4.1.1) or treatment failure

Documentation of these criteria will be submitted to the Medical Monitor for review. Investigators may discuss the appropriateness of OLT directly with the Medical Monitor if needed. For patients who initiate OLT based on the Week 76 assessment, the first OLT visit (OLT Day 1) will occur on Week 80.

Additionally, patients who, during blinded treatment after Week 80, experience a loss of adequate response requiring intensification of therapy and without unmanageable treatment-emergent adverse events may initiate OLT once 60 days have elapsed from the most recent obinutuzumab or placebo infusion.

During OLT, patients will receive obinutuzumab 1000 mg on OLT Day 1 and OLT Weeks 2, 24, 26, 52, and once every 6 months thereafter. Background immunosuppression, including doses of corticosteroids and MMF, may be adjusted at the investigator's discretion beginning at OLT Day 1.

During OLT, investigators should regularly review the study safety plan (see Section 5.1), including the risks associated with obinutuzumab (see Section 5.1.1) and management of specific adverse events that may be related to obinutuzumab (see Section 5.1.3.3), to ensure the patient has not developed a condition that would warrant discontinuation of obinutuzumab infusions. Prior to resuming OLT after treatment

interruption, investigators should refer to Section 5.1.3.2 to ensure the patient meets the criteria for resuming treatment.

After study unblinding (see Section 3.1.5), no further OLT will be initiated and ongoing OLT will be discontinued after OLT Week 52. Subsequent access to obinutuzumab may occur through post-trial access (see Section 4.3.4).

Patients who discontinue OLT will enter SFU (see Section 3.1.4).

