4.4.4.1.1 Corticosteroid Rescue

Use of high doses of corticosteroids shortly before the primary endpoint at Week 76 may affect this assessment and should be avoided. Administration of any of the following from Week 64 onward will be considered rescue:

- Methylprednisolone ≥ 100 mg IV or equivalent
- Prednisone ≥ 20 mg/day or equivalent (mean dose) over any 2-week period

Patients who receive corticosteroid rescue will be treated as nonresponders. Patients who receive rescue with corticosteroids alone are not required to discontinue obinutuzumab or placebo infusions and may be eligible for OLT if all eligibility criteria are met (see Section 3.1.3).

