4.7 TREATMENT, PATIENT, STUDY, AND SITE DISCONTINUATION

4.7.1 Study Treatment Discontinuation

Patients must permanently discontinue obinutuzumab or placebo infusions if they experience any of the following:

- Any medical condition that the investigator or Sponsor determines may jeopardize the patient's safety if study treatment is continued
- Investigator or Sponsor determination that treatment discontinuation is in the best interest of the patient
- Pregnancy
- Grade 4 IRR or recurrence of Grade 3 IRR upon re-challenge
- Grade 3 or 4 neutropenia that does not resolve to Grade ≤2 within 8 weeks
- Grade 3 or 4 thrombocytopenia (not due to SLE) that does not resolve to Grade ≤2 within 8 weeks
- Hepatitis B reactivation despite the initiation of the appropriate anti-viral therapy
- Receipt of rescue therapy as defined in Section 4.4.4.1

The primary reason for study treatment discontinuation should be documented on the appropriate eCRF. Patients who discontinue study treatment prematurely will not be replaced. Any patient who discontinues treatment should continue to undergo protocol-mandated visits.

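### For one group of patients with corticosteroid-only rescue between Weeks 64 and 76, the protocol's rules conflict on what happens at Week 80

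*Protocol*

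**What the plan says.** Corticosteroid rescue is defined in Protocol Section 4.4.4.1.1 by dose and time: "Administration of any of the following from Week 64 onward will be considered rescue". The plan then treats it in two ways.

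**Places that exempt it**
- Table 1 (Section 3.1.2): the last row, which leads to study follow-up, lists rescue therapy with the footnote "Except corticosteroid-only rescue (see Section 4.4.4.1".
- Section 3.1.3, open-label treatment (OLT) criteria: "No rescue therapy (except corticosteroid-only rescue; see Section 4.4.4.1.1) or treatment failure".
- Section 4.4.4.1.1: "Patients who receive rescue with corticosteroids alone are not required to discontinue obinutuzumab or placebo infusions". SAP Section 4.2.1.1 repeats this.

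**Places that do not**
- Section 3.1.2, adequate-response list: "No receipt of rescue therapy or treatment failure". SAP Section 4.6.6 copies the list unchanged. A separate item in the same list already covers steroid use: "No need for high-dose corticosteroids".
- Section 3.3.1, under Other Response: patients who receive rescue therapy go to follow-up on standard of care.
- Section 4.7.1, reasons for mandatory permanent discontinuation: "Receipt of rescue therapy as defined in Section 4.4.4.1".

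Section 3.1.4 adds a default. Anyone who neither continues blinded infusions nor enters OLT on the Week 76 assessment goes to follow-up.

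**The concern.** The Week 76 assessment sorts patients into continued blinded infusions, OLT or follow-up. If the rules for one kind of patient disagree, sites that read different sections will treat the same patient differently at Week 80.

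That also matters for analysis. SAP Section 4.6.6 compares the arms among patients who met adequate response and stayed on blinded treatment. If entry to that group depends on which section a site followed, its composition is partly a matter of local interpretation.

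Such a patient is plausible. Appendix 5 permits higher prednisone doses for extrarenal flares for up to 2 weeks, with tabulated starting doses of 20 to 60 mg/day. Two full weeks at the lowest of these gives a mean of (14 × 20)/14 = 20 mg/day, which already reaches the rescue threshold of 20 mg/day over a 2-week period. This can happen while the renal measures are in range.

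**Working it through.** The question is one of textual consistency, and no sample size, power or alpha figure is involved. The check is to route one patient through the rules.

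**Patient A:** corticosteroid-only rescue between Weeks 64 and 76; UPCR and eGFR criteria met; no current need for high-dose steroids; no need for intensification; no other rescue, treatment failure or unmanageable adverse event.

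1. *Adequate response (Section 3.1.2).* Read literally, A fails, because the rescue item has no steroid exception.
2. *OLT (Table 1 and Section 3.1.3).* A fails, because OLT requires "Current need for intensification of therapy".
3. *Last row of Table 1.* The footnote removes A from the rescue trigger. The treatment-failure trigger does not apply either, since Section 4.4.4.2 leaves out steroid-only rescue. No other trigger is met.

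So no row of Table 1 fits. The outcome depends on the reading taken:

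| Reading | Route for patient A |
|---|---|
| List as written; 4.7.1 limited to non-steroid rescue | No Table 1 row; follow-up by the Section 3.1.4 default |
| Steroid exception read into the list; 4.7.1 limited to non-steroid rescue | Blinded infusion at Week 80 |
| 4.7.1 applied to steroid rescue | Permanent stop, then follow-up as an early discontinuation |

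**Timing.** Blinded infusions fall at Day 1, at Weeks 2, 24, 26, 50, 52 and 80, and every 6 months after that. None falls between Weeks 64 and 76. For rescue in that interval, the statement in Section 4.4.4.1.1 that infusions need not stop can first take effect at Week 80, which is where the Section 3.1.2 list withholds them.

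**Patient B, for comparison:** the same rescue, with improvement from baseline, an inadequate response and a need for intensification. Table 1, Section 3.1.3 and Section 4.4.4.1.1 all allow OLT. Only the unqualified wording of Sections 3.3.1 and 4.7.1 disturbs that route.

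**SAP Section 4.6.6.** The opening text and the estimand restrict the analysis to patients who meet the adequate-response criteria, and the criteria list has no steroid exception. The population definition at the end of the section asks only that patients continue blinded treatment and reach the visit by the cutoff. If a site continues A under Section 4.4.4.1.1, A is inside the second definition and fails the first.

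**The case against.** The strongest reply is that the sections can be read in order without contradiction. Not having to stop infusions does not make a patient an adequate responder. Steroid rescue could count against adequacy at Week 76 without barring OLT, and Section 3.1.4 catches everyone else. The permission in Section 4.4.4.1.1 also keeps a use for rescue after Week 80. Table 1 is guidance applied by the investigator, who may consult the Medical Monitor. Nor are the steroid rules its only gap: an unrescued patient with some improvement, an inadequate response and no need for intensification fits no row either.

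Much of this stands. Patient A does have a destination. But the reply makes Table 1's footnote ineffective for A, since the exempted patient goes to follow-up anyway. It also leaves open why the adequate-response list alone lacks the exception. Case-by-case discussion is not a stated rule.

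A reader might also infer that Section 4.7.1 flatly contradicts Section 4.4.4.1.1. The documents do not support that. Section 4.7.1 points to Section 4.4.4.1, whose therapy list omits corticosteroids and whose discontinuation sentence refers to the steroid exception. The wider reading is possible, because Section 4.3.2.1 and the Table 1 footnote cite Section 4.4.4.1 for corticosteroid rescue. The conflict is largely resolved and remains a secondary wording point.

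On the SAP, the population definition follows actual continuation, and adequacy is as the investigator assesses it. A data set can therefore be built. What it represents still depends on the rule that each site used.

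**Conclusion.** The conflict is real but narrow. It concerns patients with steroid-only rescue between Weeks 64 and 76 who otherwise meet the adequate-response criteria and need no intensification. For them, Section 3.1.2 withholds adequate response, while the Table 1 footnote, Section 4.4.4.1.1 and SAP Section 4.2.1.1 treat the rescue as no reason to stop. Section 3.3.1 adds a second inconsistency by omitting the exception that Sections 3.1.3 and 4.4.4.1.1 contain.

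Two broader conclusions are tempting and not supported. One is that any patient rescued with steroids from Week 64 has no consistent pathway: on the text as written, those who improved, responded inadequately and need intensification have an OLT route in three agreeing places. The other is that the main results are at risk: steroid rescue from Week 64 counts as non-response for the primary endpoint under every reading, and the other Week 76 endpoints do not depend on the Week 80 route.

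The consequences are treatment routing at Week 80 and membership of a post-Week 76 population that the SAP itself calls supportive and exploratory. The documents give no rate of corticosteroid rescue, so the number of patients cannot be estimated. The correction is still worth making, because it decides who receives an infusion and costs only wording.

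**What to change.** The sponsor should decide which rule governs corticosteroid-only rescue and state it once, explicitly. The same rule should then appear in the Section 3.1.2 adequate-response list, Table 1 and its footnote, Section 3.3.1 (Other Response), Section 4.4.4.1.1 and Section 4.7.1. This review takes no position on which rule is right. The text should say where a patient goes who was rescued with steroids alone between Weeks 64 and 76 and needs no intensification, so that the route does not rest on the Section 3.1.4 default.

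In SAP Section 4.6.6, the criteria list and the population definition should both be aligned with that rule, so that a patient cannot satisfy one and fail the other. A count by arm of patients with steroid-only rescue between Weeks 64 and 76, with their Week 80 destination, would show how many are involved.

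The cost is protocol and SAP wording plus one small summary. Sample size, alpha, visits and the Week 76 analyses do not change.
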